## **9. TREATMENT OF PATIENTS**

### **9.1. Select Management Guidelines**

The following guidelines apply to the management of study participants:

#### **9.1.1. Management of Fluid Status**

Specific risk mitigation procedures will be employed to reduce the potential for bardoxolone methyl-induced fluid overload. Laboratory data, as well as BNP and/or NT-proBNP, will also be used to monitor fluid status.

Additionally, patients will be monitored for rapid weight gain suggestive of fluid overload. Patients will be given a Sponsor-provided scale to use at home to monitor their weights daily during the first 8 weeks of the treatment period. Patients who experience a 5-pound (2.3 kilogram) or greater increase in weight since their Day 1 weight during the first 8 weeks of the treatment period will be instructed to stop taking their study medication immediately and return to the clinic for an unscheduled physical examination and laboratory assessment by the investigator. Patients may not restart their study medication until the investigator has completed and documented an assessment of fluid overload.

Investigators should advise patients to watch for signs and symptoms of fluid overload. Patients should be informed to notify their physicians immediately if they experience swollen feet, chest pain, shortness of breath with mild exertion or while lying down, or other relevant symptoms. The investigator should immediately assess symptoms of fluid overload and determine appropriate medical management, as necessary, including whether stopping drug administration will be required. At the earliest sign of worsening or new onset peripheral edema, or other signs and symptoms of acute volume overload, investigators will also be expected to determine if changes to a patient's diuretic regimen is needed.

#### **9.1.2. Management of Elevated Transaminase Levels (ALT and/or AST)**

Transaminases should be monitored following patient's standard of care. Nearly all instances of elevated transaminases are expected to be asymptomatic. Transaminase levels (as well as total bilirubin [TBL], GGT, alkaline phosphatase, and INR) will be checked within 48 to 72 hours during an unscheduled visit if the following occurs:

- ALT or AST levels > 3X ULN.

Testing will be repeated every 72 to 96 hours until transaminase levels are below 3X the ULN for at least one week or until the patient withdraws consent.

Study drug administration will be permanently discontinued if any of the following occurs:

- ALT or AST > 8X ULN;
- ALT or AST > 5X ULN for more than 2 weeks;
- ALT or AST > 3X ULN and (TBL > 2X ULN **or** INR > 1.5);

- ALT or AST > 3X ULN with the appearance of fatigue, nausea, vomiting, right upper quadrant pain or tenderness, fever, rash, and/or eosinophilia (> 5%).

The hepatobiliary tree must be visualized (*e.g.*, ultrasound, magnetic resonance imaging) and assessed if a patient discontinues taking study drug secondary to elevated transaminase levels. Additional tests/studies may be warranted depending on the clinical presentation.

#### **9.1.3. Management of Muscle Spasms**

Basic symptomatic relief is the first step in managing muscle spasm, including walking, adequate hydration, wearing socks, and stretching before bedtime. Assessment of levels of electrolytes such as magnesium, calcium and potassium as part of patient's standard of care may indicate the need for replacement. If vitamin D levels are low, supplementation may be warranted. Muscle relaxants may also help relieve symptoms.

#### **9.1.4. Weight Loss**

Ongoing assessments to ensure that the patient is receiving adequate nutrition and consideration of other etiologies of weight loss may be warranted for patients receiving bardoxolone methyl.

#### **9.1.5. Hypomagnesaemia**

In instances where a patient experiences hypomagnesaemia (evaluated as part of patient's standard of care), defined as serum magnesium less than 1.3 mEq/L (0.65 mmol/L), consideration should be given to repletion of serum magnesium.

#### **9.1.6. Nausea**

Nausea may occur with higher doses of bardoxolone methyl. Nausea AEs are typically mild and reversible within a few weeks after treatment initiation. If symptoms will not resolve, dose de-escalation, with consultation of the medical monitor, may be necessary.

## 9.2. Description of Study Drug

Bardoxolone methyl (RTA 402) drug product information is shown in [Table 4](#).

**Table 4: Bardoxolone Methyl Drug Product Information**

Description	Bardoxolone methyl capsule (5 mg, 10 mg)
Ingredients	Bardoxolone methyl Methacrylic Acid – Ethyl Acrylate Copolymer [REDACTED] Type A Silicified Microcrystalline Cellulose Hydroxypropyl Methylcellulose Lactose Monohydrate Sodium Lauryl Sulfate Colloidal Silicon Dioxide Magnesium Stearate Gelatin capsules Titanium Dioxide [REDACTED]
Route of Administration	Oral

## 9.3. Concomitant Medications

### 9.3.1. Excluded Medications

No other investigational drug or device should be taken as part of an interventional study during the conduct of this study.

Patients who take investigational drug or device during the study should not discontinue study drug solely on this basis. Consultation with the medical monitor should occur prior to study drug discontinuation or withdrawing a patient from the study.

### 9.3.2. Permitted Medications

Pulmonary arterial hypertension-specific background therapy should be taken as clinically indicated and prescribed by the physician for the duration of the study.

Refer to [Section 9.10.15](#) for guidelines on oxygen use during 6MWTs. Initiation of supplemental long-term oxygen therapy (oxygen application for more than 30 consecutive days) or persistent modification of a pre-existing supplemental long-term oxygen therapy (*i.e.*, need for a persistent increase of the amount of delivered oxygen for more than 30 days) due to worsening PAH is permitted.

Diuretics may be prescribed as clinically indicated throughout the study. Any changes to the doses of oxygen or diuretics throughout the course of the study must be recorded in the electronic case report form (eCRF).

#### **9.4. Treatment Compliance**

The investigator or his/her designated and qualified representatives will only dispense study drug to patients enrolled in the study in accordance with the protocol. The study drug must not be used for reasons other than that described in the protocol.

#### **9.5. Randomization**

Not applicable.

#### **9.6. Blinding**

Not applicable.

#### **9.7. Unscheduled Visits**

Unscheduled visits are allowed for the following reasons:

- Assessment of weight gain per [Section 9.1.1](#);
- Management of an AE or SAE;
- Performance of additional laboratory tests for clinically abnormal laboratory test values or to confirm a possible pregnancy;
- Dose de-escalation;
- Any time the investigator feels that it is clinically appropriate for patient safety.

At a minimum, unscheduled visits should include collection of AEs, concomitant medications and vital signs. Additional conversations may be necessary with the medical monitor following an unscheduled visit to assess patient safety.

#### **9.8. Pregnancy**

##### **9.8.1. Women of Childbearing Potential**

Women of childbearing potential (WOCBP) are those who are not surgically sterile (no history of bilateral tubal ligation, hysterectomy, or bilateral salpingo-oophorectomy), do not have fallopian inserts with confirmed blockage, have not had reproductive potential terminated by radiation, and are not postmenopausal for at least 1 year.

##### **9.8.2. Methods of Birth Control**

While taking study drug and until 30 days following administration of the final dose of study medication, WOCBP must practice one of the following acceptable methods of birth control:

- Use of hormonal contraceptives (oral, parenteral, vaginal, or transdermal) for at least 90 days prior to start of study drug administration;
- Use of an intrauterine device;

- Abstain from sexual intercourse completely. Complete abstinence from sexual intercourse is only acceptable if it is the preferred and usual lifestyle of the individual. Periodic abstinence is not permitted.

While taking study drug and until 30 days after the final dose of study medication is taken, males who have female partners of childbearing potential must practice one of the following methods of birth control:

- Have had a vasectomy (at least 6 months earlier);
- Partner use of an intrauterine device;
- Partner use of hormonal contraceptives (oral, parenteral, vaginal or transdermal) for at least 90 days prior to start of study drug administration;
- Abstain from sexual intercourse completely. Complete abstinence from sexual intercourse is only acceptable if it is the preferred and usual lifestyle of the individual. Periodic abstinence is not permitted.

### **9.8.3. Suspected Pregnancy**

During the study, all WOCBP must be instructed to contact the investigator immediately if they suspect they might be pregnant (*e.g.*, late or missed menstrual period). Male patients must be instructed to contact the investigator if a sexual partner suspects she may be pregnant.

If a patient or investigator suspects that the patient may be pregnant, the study drug must be withheld until the results of a serum pregnancy test are available. If the serum pregnancy test confirms the pregnancy, the patient must permanently discontinue taking study drug. The investigator must immediately report to the medical monitor a pregnancy associated with study drug exposure. The early discontinuation protocol-required procedures outlined for End-of-Study visits must be performed on the patient.

Pregnancy is not considered an AE; however, the investigator must follow a pregnant patient, or the pregnant female partner of a male patient (if consenting), and report follow-up information regarding the course of the pregnancy, including perinatal and neonatal outcome. Infants resulting from such pregnancies should be followed for a minimum of 8 weeks. Reata or designee may contact the investigator to request additional information throughout the course of the pregnancy.

The following pregnancy outcomes must be considered SAEs and will require additional reporting in the eCRF and reported as an SAE:

- Congenital anomaly/birth defect;
- Stillbirth;
- Spontaneous miscarriage.

## **9.9. Serious Toxicities**

In the case of serious toxicities, the investigator may choose to interrupt treatment with bardoxolone methyl. A single dose reduction (from 10 mg to 5 mg) is permitted if clinically indicated to manage tolerability issues. Once a patient's dose has been reduced, that dose must

be maintained. Patients who resume therapy after an interruption will follow the originally planned study schedule.

## **9.10. Study Procedures**

The following sections describe each assessment. The timing of these assessments is noted in [Table 3](#). All Day 1 procedures, except AE assessments, should be completed prior to administration of first dose of study drug.

### **9.10.1. Informed Consent**

Written informed consent (see [Section 15.3](#)) must be obtained from the patient before any study-related procedures are performed, and again if there is a change in the study procedures that would affect the patient's willingness to participate.

### **9.10.2. Inclusion/Exclusion**

Inclusion and exclusion criteria must be reviewed as indicated in [Table 3](#). Patients must meet all of the inclusion and none of the exclusion criteria for entry in the study.

### **9.10.3. Prior and Current Concomitant Medications**

The name, dose, and frequency must be recorded for all medications that the patient is taking. All allowed and excluded medications should be recorded including all prescription drugs, herbal products, vitamins, minerals, and over-the-counter medications. Trade or generic drug names should be used where possible. Concomitant medications will be reviewed as indicated in [Table 3](#) and all changes will be recorded.

### **9.10.4. Current PAH Background Medications**

The name, dose, and frequency must be recorded for all PAH background medications that the patient is taking. PAH background medications are those that have been approved by the US Food and Drug Administration (FDA) or the local health authority for the treatment of PAH. Trade or generic drug names should be used where possible. PAH background medications will be reviewed as indicated in [Table 3](#) and all changes will be recorded.

### **9.10.5. Weight and Body Mass Index**

Weight must be measured as indicated in [Table 3](#). Body mass index (BMI) will be calculated in the eCRF each time the weight is recorded. Patients will use Sponsor-provided scales to measure weight at home. Patients will be instructed to stop administering study drug and contact the investigator if their daily weight increases per the criteria outlined in [Section 9.1.1](#). Patients will be provided instructions within the Informed Consent Form to help ensure consistent weight collection throughout the study.

### **9.10.6. Vital Sign Measurements**

Vital sign measurements include the patient's heart rate (beats/minute taken for at least 15 seconds), respiration rate, and body temperature. Blood pressure should be taken after the patient has rested in a sitting position for at least 5 minutes. The same arm (usually the non-

dominant arm) and the appropriate size cuff should be used for each measurement. Vital sign measurements should be taken as indicated in [Table 3](#).

#### **9.10.7. Physical Examination**

A comprehensive physical examination must be performed by a physician, physician assistant, or registered nurse practitioner as indicated in [Table 3](#) and as documented within the table footnotes. The examination must include the following organ or body system assessments: head, eyes, ears, nose, throat, musculoskeletal, cardiovascular, lymphatic, respiratory, abdomen, skin, extremities, and neurological. Assessments of any specific signs or symptoms reported by the patient must also be performed and documented along with any other findings of note. Clinically significant findings at Day 1 must be recorded as medical history. Following the examination on Day 1, new or changed physical examination findings meeting the criteria for an adverse event must be recorded as an adverse event. If possible, the same individual should perform each physical examination on a patient during the study.

#### **9.10.8. Pregnancy Test**

WOCBP (see [Section 9.8](#)) will complete a pregnancy test as indicated in [Table 3](#), or at any time if pregnancy is suspected. Negative test results are required on Day 1 before study drug administration. Any patient who becomes pregnant during the study must discontinue taking study drug immediately. See [Section 9.8.3](#) for a description of procedures to be followed in case of pregnancy.

#### **9.10.9. Study Drug Administration**

Patients should self-administer one capsule orally, once a day, preferably in the morning, as indicated in [Table 3](#). A vomited dose must not be replaced. A double dose (*e.g.*, missed dose from previous day and dose for current day) must not be taken.

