### 5.2.2. Fluid Overload

Similar to endothelin receptor antagonists in certain patient populations, including bosentan in advanced congestive heart failure and avosentan in advanced CKD, bardoxolone methyl treatment was found to be associated with an increased risk for fluid overload and heart failure hospitalizations in a Phase 3 trial (BEACON), which enrolled patients with Stage 4 CKD (eGFR of 15-29 mL/min/1.73 m^2) and type 2 diabetes. The overall increased risk for fluid overload and heart failure events with bardoxolone methyl appeared to be limited to the first three to four weeks after initiation of treatment. Elevated B-type natriuretic peptide (BNP) and prior hospitalization for heart failure were identified as risk factors that contributed to increased risk for these events. The increased risk for these events from bardoxolone methyl treatment had not been observed in six previous CKD studies, which were conducted mostly in patients with Stage 3b CKD (eGFR of 30-44 mL/min/1.73 m^2), patients with hepatic dysfunction, cancer patients, or healthy volunteers.

Review of admission notes and narrative descriptions for heart failure hospitalizations in BEACON indicates that heart failure in bardoxolone methyl-treated patients was often preceded by rapid fluid weight gain (several kilograms within the first weeks of treatment initiation) and was not associated with acute renal decompensation or acutely reduced left ventricular contractility. Available data from BEACON and other studies suggest that bardoxolone methyl treatment can differentially affect hemodynamic status according to the clinical condition of patients and likely promotes fluid retention in patients with more advanced renal dysfunction and other recognized risk factors associated with heart failure at baseline.

In a Phase 2 dose-ranging study of the efficacy and safety of bardoxolone methyl in patients with PH (LARIAT), risk mitigation procedures were employed to reduce the potential for bardoxolone methyl-induced fluid overload; these procedures excluded patients with the identified risk factors and ensured close monitoring for fluid retention within the first month of treatment. To date, the risk for acute fluid overload adverse events (AEs) with bardoxolone methyl in late-stage CKD patients has not been observed in PAH patients.

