### **7.3.1. Dose Escalation and Dose De-Escalation**

Patients will start dosing at 10 mg of bardoxolone methyl every other day, then begin once daily dosing at Week 4 unless contraindicated clinically. The investigator should discuss any reasons for not dose-escalating to once daily dosing at Week 4 with the medical monitor.

Dose de-escalation is permitted during the study and the investigator may choose to decrease the patient's dose to 5 mg if clinically indicated. Reasons for dose de-escalation should be discussed with the medical monitor prior to changing dose. Once a patient's dose has been decreased to 5 mg, they cannot dose-escalate back to 10 mg of bardoxolone methyl.

Unscheduled visits due to dose de-escalation should include assessments detailed in [Section 9.7](#).

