**Table 3: Schedule of Assessments**

Assessment \ Study Week (Day)	Day 1 a	Week 1 (Phone) Day 3±2	Week 1 Day 7±3	Week 2 (Phone) Day 10±2	Week 2 Day 14±3	Week 3 (Phone) Day 21±2	Week 4 Day 28±3	Week 4 (Phone) Day 31±2	Week 5 (Phone) Day 38±2	Week 6 Day 42±3	Week 8 Day 56±3	Week 24±3, Every 24 Weeks	End of Study Visit b
Informed consent	X												
Inclusion/Exclusion	X												
Prior and Concomitant medications	X c	X	X	X	X	X	X	X	X	X	X	X	X
Current PAH background medications	X c	X	X	X	X	X	X	X	X	X	X	X	X
Weight at home	X	X	X	X	X	X	X	X	X	X	X		
Weight in clinic	X c		X		X		X			X	X	X	X
Vital sign measurements	X c		X		X		X			X	X	X	X
Physical examination	X c		X		X		X			X	X	X	X
Pregnancy test d	X c											X	
Dispense study drug	X						X					X	
Collect study drug							X					X	X
Telephone contact		X		X		X		X	X				
Adverse event collection	X c	X	X	X	X	X	X	X	X	X	X	X	X
Clinical Chemistries f	X c		X		X		X			X	X	X	X
BNP and/or NT-Pro BNP	X c		X		X		X			X	X	X	X
6-min walk test	X c											X	X
Dyspnea and fatigue g	X c											X	X
WHO functional class	X c											X	X

a On Day 1, all procedures should be performed before study drug administration for patients who are treatment-compliant and have previously participated in clinical studies with bardoxolone methyl.

b After the Week 24 visit, patients will continue to be assessed in person every 24 weeks. The End of Study visit should occur within 30 days after the patient receives their final dose of study medication under this protocol. Patients who will be discontinued from the study prior to the completion of the study must also complete all End-of-Study assessments.

c Day 1 assessments should be performed as part of End-of-Treatment or Follow-up visit procedures from a prior study with bardoxolone methyl.

d A serum pregnancy test will be performed at any point in time if a pregnancy is suspected. All other pregnancy assessments will be urine pregnancy tests. Additional pregnancy assessments will be performed more frequently if required by local law or requested by local health authorities or IRBs/ECs.

e AE assessments on Day 1 should be performed following study drug administration.

f Clinical chemistries will be analyzed locally.

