#### **9.10.10. Study Drug Dispensation and Collection**

Study drug will be dispensed to the patient and collected from the patient as indicated in [Table 3](#). The patient will be dispensed 1 or more treatment kits at Day 1, Week 4, Week 24, and every 24 weeks thereafter for the duration of the study. Dispensed treatment kits from each visit should be returned to the site for collection at the subsequent visit.

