#### **9.10.11. Telephone Contact**

Patients will be contacted by telephone as indicated in [Table 3](#). Patients will be asked about their body weight and other signs of fluid retention, as well as AEs and any changes to concomitant medications. If fluid retention is suspected, the patient must be brought into the clinic and evaluated by the investigator as soon as possible, as detailed in [Section 9.1.1](#).

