### 10.4. Study Drug Administration

Please refer to [Section 9.10.9](#) for details on study drug administration. Clear instructions will be provided to the patient regarding the number and type of capsules to be ingested at each study drug administration time point listed in [Table 3](#). Patients must be instructed to continue taking study drug unless: (1) patient has been otherwise instructed by the investigator or (2) the patient has been formally discontinued from the study.

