4. STUDY DESIGN

4.1. Summary of Study Design

RANGER examines the long-term safety and tolerability of bardoxolone methyl in qualified patients with pulmonary hypertension (PH) following completion of previously controlled clinical studies with bardoxolone methyl. Patients and investigators are not unblinded to study treatment from previously controlled clinical studies upon entering the RANGER study.

Qualified patients receive open label bardoxolone methyl (10 mg) every other day, then begin once daily dosing at Week 4 (unless contraindicated clinically) and continue until the drug is available through commercial channels or until patient withdrawal, whichever is sooner. Dose de-escalation (down to 5 mg) is permitted during the study if indicated clinically. Refer to Protocol Section 7.3.1 for additional details on dose de-escalation.

All patients in RANGER follow the same visit and assessment schedule. RANGER Day 1 is defined as the first day treatment is dispensed to the patient for this trial, following completion of previously controlled clinical studies. All other RANGER visits are relative to RANGER Day 1. Patients are scheduled for in-person assessments during treatment in RANGER at Day 1, Week 1, Week 2, Week 4, Week 6, Week 8, Week 24, and every 24 weeks thereafter. Patients are also assessed by telephone contact on Days 3, 10, 21, 31, and 38.

Since patients from previously controlled clinical studies will be followed continuously within the study (i.e., seamless rollover), eligibility for the RANGER study is assessed at the follow-up visit or End-of-Treatment visit and a separate screening visit is not required.

[figure not shown]
Patients from the CATALYST study:

Day 1 of this extended access study coincides with the Week 28 follow-up visit for patients from CATALYST (402-C-1504, NCT02657356, EudraCT 2016-000196-24). If this extended access program is not yet open for enrollment at the time of a patient's Week 28 visit, the Day 1 visit (i.e., enrollment) must occur within 30 days of site activation. Exceptions allowing CATALYST patients who have completed 24 weeks of treatment to schedule their follow-up assessments prior to Week 28 and still be considered eligible for this open-label study should be discussed with the Chief Medical Officer at Reata, or designee, and are considered on a case-by-case basis.

Patients from the LARIAT study:

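### Protocol 9.10.9 instructs once-daily dosing with no exception before Week 4, against the every-other-day start set elsewhere, and the SAP 9.2 compliance ratio would score that error as better compliance

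*Protocol*

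**What the plan says.** The regimen is set in Protocol 7.3.1: "Patients will start dosing at 10 mg of bardoxolone methyl every other day, then begin once daily dosing at Week 4 unless contraindicated clinically". The protocol synopsis, Protocol 7.1 and the SAP synopsis agree, and SAP 4.1 has "Qualified patients receive open label bardoxolone methyl (10 mg) every other day, then begin once daily dosing at Week 4".

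Protocol 9.10.9, the section on how the drug is taken, says "Patients should self-administer one capsule orally, once a day, preferably in the morning" and refers to Table 3 for timing. Table 3 has rows such as "Dispense study drug" and one for collection, but no row for dosing frequency. Protocol 10.4 sends the reader back to 9.10.9 for details and adds that "Clear instructions will be provided to the patient regarding the number and type of capsules to be ingested". Those patient instructions are not in the documents.

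On supply, Protocol 9.10.10 says "The patient will be dispensed 1 or more treatment kits at Day 1, Week 4, Week 24, and every 24 weeks thereafter". Protocol 10.2 gives 90 capsules per 10 mg bottle, and Protocol 10.5 has returned capsules counted per bottle at each visit.

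SAP 9.2 defines compliance as 100 times doses received over doses dispensed, where doses received are doses dispensed minus doses returned. Its by-visit dose table splits patients by strength only (5 mg or 10 mg).

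**The concern.** This is a contradiction in current, operative dosing text, and the cross-references do not repair it. Table 3 is silent on frequency, 10.4 points back to 9.10.9, and the double-dose example in 9.10.9 (yesterday's missed dose plus today's) presumes daily dosing. The SAP's statement that it governs over the protocol covers planned analyses, not dosing.

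A site following 9.10.9 literally would reach the target dose of 10 mg daily about four weeks early, inside the 8 weeks that the protocol monitors for fluid overload. The pre-Week 4 telephone contacts are not described as checking frequency: "Patients will be asked about their body weight and other signs of fluid retention, as well as AEs and any changes to concomitant medications". The first scheduled drug collection is at Week 4.

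The planned analysis would not expose the error. A dispensed-dose denominator measures how much of the supply was kept, not adherence to the regimen. A fully adherent patient given surplus capsules scores below 100%, and overdosing raises the score. In the by-visit dose table, 10 mg every other day and 10 mg daily fall in the same row.

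**Working it through.** The documents state no capsule count, so there is no planned figure to reproduce. The count below is direct.

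**Inputs.** First dose on Day 1. Week 4 visit on Day 28±3 (Table 3), with the switch that day or the next, so the first daily dose falls on day *s* = 25 to 32. One 10 mg capsule per dose. Full adherence and no interruptions are assumed.

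**Up to the switch.** Every-other-day doses fall on odd days, so the intended count is (*s* − 1)/2 rounded up. The literal 9.10.9 count is *s* − 1.

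| *s* | Intended | Literal | Extra | Ratio |
|---|---|---|---|---|
| 25 | 12 | 24 | 12 | 2.00 |
| 26 | 13 | 25 | 12 | 1.92 |
| 27 | 13 | 26 | 13 | 2.00 |
| 28 | 14 | 27 | 13 | 1.93 |
| 29 | 14 | 28 | 14 | 2.00 |
| 30 | 15 | 29 | 14 | 1.93 |
| 31 | 15 | 30 | 15 | 2.00 |
| 32 | 16 | 31 | 15 | 1.94 |

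The excess is 12 to 15 capsules, or 120 to 150 mg.

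**Over fixed periods.** Intended intake to day *D* is the count above plus (*D* − *s* + 1); literal intake is *D*.

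- Day 28: 28/16 = 1.75 (*s* = 25 or 26), 28/15 = 1.87 (*s* = 27 or 28), 28/14 = 2.00 (*s* ≥ 29).
- Day 56: 56/44 = 1.27 to 56/41 = 1.37.
- Day 168 (Week 24): 168/156 = 1.08 to 168/153 = 1.10.
- Day 336 (Week 48): 336/324 = 1.04 to 336/321 = 1.05.
- Never escalated, Day 168: 168/84 = 2.00, with no dilution.

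**Effect on SAP 9.2 compliance.** For two patients dispensed the same supply the denominator cancels, so the Day 168 and Day 336 ratios are also the ratios of their compliance scores, whatever the kit count.

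The absolute scores depend on kit numbers, which the documents do not fix. As an illustration, take *s* = 29 and 90-count kits:

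| Assumed kits (Day 1 / each later dispensing) | Dispensed to Week 24 / Week 48 | Perfect adherence, Week 24 / Week 48 | Daily from Day 1, Week 24 / Week 48 |
|---|---|---|---|
| 1 / 2 (minimum) | 270 / 450 | 154/270 = 57.0% / 322/450 = 71.6% | 168/270 = 62.2% / 336/450 = 74.7% |
| 2 / 3 (one extra) | 450 / 720 | 154/450 = 34.2% / 322/720 = 44.7% | 168/450 = 37.3% / 336/720 = 46.7% |

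In each case the patient who followed the regimen exactly scores well below 100% and below the patient who took too much.

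**What the Week 4 return can show.** From one 90-count kit under full adherence, with the visit on Day 25, 28 or 31 and the visit-day dose taken from the old bottle or not:

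- every other day: 12 to 16 taken, 74 to 78 returned;
- daily: 24 to 31 taken, 59 to 66 returned.

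The ranges do not overlap. Missed doses would blur the distinction in a daily doser.

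**The case against.** The strongest reply is that 9.10.9 is a short handling paragraph containing a missed edit, while 7.3.1 is the section that sets frequency and every other statement of the regimen agrees with it. A site dosing daily from Day 1 would find nothing to escalate at Week 4. Protocol 10.4 promises separate patient instructions, 13.2 provides telephone monitoring that instructions are understood and applied, and Table 3 has clinic visits at Days 7 and 14 with weight, chemistry and BNP. Non-escalation has to be discussed with the medical monitor, so sustained daily dosing in such a patient is unlikely, and Week 4 returns should reveal it. No passage says why dosing starts every other day, 10 mg daily is the target dose, LARIAT entrants had already received the drug, and 5.2.2 says that the acute fluid-overload risk seen "in late-stage CKD patients has not been observed in PAH patients". SAP 9.2 also reports total dose in mg and days of exposure, and its denominator would be a problem whatever 9.10.9 said.

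Most of this stands as a limit on likelihood. No misdosing is shown, and the safeguards make it less probable. None of it makes the instruction correct. Total dose and duration are whole-treatment figures with no expected dose beside them, so they dilute an early doubling just as the compliance ratio does. The SAP 9.2 weakness is indeed separable; it belongs here because it is the summary a reader would use to judge whether dosing went to plan.

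**Conclusion.** The concern holds and should be fixed. Protocol 9.10.9 is wrong as written: followed literally it gives 1.92 to 2.00 times the intended intake up to the Week 4 switch, 12 to 15 extra 10 mg capsules, and continued doubling in any patient not escalated. These figures assume a first dose on Day 1, full adherence, no interruptions and a switch at the Week 4 visit or the day after.

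The safety consequence is conditional on sites having followed that sentence, which the documents do not show. The reporting consequence remains after the termination on March 30, 2020. SAP 9.2 compliance does not measure adherence, and it would score early daily dosing 1.08 to 1.10 times a perfect patient at Week 24 and 1.04 to 1.05 times at Week 48. The percentage illustrations rest on assumed kit counts; the ratios do not.

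The size of the affected group is unknown. The SAP's revision chronology says Amendment 2 (July 2018) changed the titration scheme, so patients who started under version 1 or 2 had a regimen these documents do not give.

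**What to change.** - **Protocol wording.** The correct text for 9.10.9 is: *one capsule every other day from Day 1 until Week 4, then one capsule once daily unless contraindicated; patients not escalated continue every other day.* The double-dose example should refer to a missed dose and the next scheduled dose.
- **Record it.** Since the study has ended, note the discrepancy and the regimen sites were actually told to use in SAP Section 11 or the study report. Section 11 already records one protocol inconsistency (the Week 1 visit) but not this one.
- **SAP 9.2 denominator.** Replace doses dispensed with doses expected under the assigned regimen and protocol version, allowing for documented interruptions and escalation status where recorded. Report Day 1 to Week 4 separately, because the whole-treatment ratio shrinks an early doubling to about 1.1 by Week 24.
- **Early intake.** Describe capsules taken before Week 4 from the Week 4 return counts.

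The cost is a short note plus some derivation work. Return counts per bottle are already recorded. No passage shows that dosing frequency was captured; where it was not, the expected dose must assume the protocol-specified frequency and say so. For patients who started under version 1 or 2, the earlier regimen has to be retrieved from those versions.
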